### g. 4-Month Follow-Up

i. Four months after baseline (approximately 2 months after post-assessment), primary and secondary outcomes will be re-assessed, in addition to key covariates and recent negative life events. Participants will be contacted using the Locator Guide and compensated \$30. These sessions will occur in person (at a private location convenient for the participant) or over Zoom as requested by participant.

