#### 3. Phase II Reimbursement

- a. Women will receive \$5 for the eligibility screener; \$15 for completing baseline measures; \$10 per session in the intervention; \$20 for the post-intervention follow-up and \$10 if they complete an additional interview; and \$30 for the 4-month follow-up.
  - i. Women are paid in cash or a Visa gift card and must sign on the iPad (via REDCap) that they have received the payment. If a virtual follow-up, the individual who provides compensation will sign. This must also be initiated, signed, and dated by the RA or GSR in charge of payment.

Subsection 2.3 - Phase II Recruitment & Treatment Overview

Table 3. O	Table 3. Overview of Phase II Assessments							
Intervention	Recruitment	Eligibility Screen	Baseline	Weekly	Post- Intervention Follow-up	4-Month Follow-up		

MSC	Info meetings with PI at RDTS	PTSD SBT a	Psychosocial questionnaires b,c,d Demographics Locator Guide e	Home practice adherence Accept & feasibility activities f	Psychosocial questionnaires b,c,d ~20-minute interview	Psychosocial questionnaire s b,c,d
TAU	Info meetings with PI at RDTS	PTSD SBT a	Psychosocial questionnaires b,c,d Demographics Locator Guide e	Short psych surveys g	Psycho-social questionnaires b,c,d	Psycho-social questionnaire s b,c,d

aPTSD, SBT=Short Blessed Test (cognitive impairment screen; >9=likely cognitive impairment); bPrimary (PTSD, substance use) & Secondary (anxiety, depression, hopelessness, loneliness) Outcomes, cMediators: emotion-regulation, self-compassion, moral injury, trauma-related guilt, trauma-related shame, craving, mindfulness; dCovariates: negative life events; cLocator Guide will be updated regularly; fUsed to provide detailed feedback on acceptability & feasibility of MSC intervention; gSurveys on attitudes, personality, other non-clinical factors. MSC=Mindful Self Compassion; TAU=Treatment as Usual

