# Section 3 – Data analytic plan

• *Power analysis*. Sample size was estimated using G\*Power and standard guidelines for testing mediation,  with α=.05, β=.80, and the standard deviation bound at ±1.91. Effect size estimates were derived from prior research on SC interventions for PTSD, which found a small-medium effect size (Cohen's d=0.2-0.5).  Particularly since the effect of MSC to reduce PTSD symptoms is emerging research, findings have been mixed regarding effect sizes for direct and indirect effects of SC interventions on PTSD, with some studies finding large effects of reduced PTSD due to SC interventions,  and others finding medium effect sizes.  (Of note, few randomized trials have been conducted).  To account for additional covariates, the clustering design,  and Type 1 error due to multiple tests, a small-medium effect size of .3 was conservatively estimated. Sample size appropriate for mediation was derived from a percentile bootstrap method, which simulations consistently show to be the most powerful test compared to similar methods (e.g., Sobel, bias-corrected bootstrap).  This yielded a final sample size of 162. Based on the team's prior research, we conservatively estimate 80% retention over time for a target enrollment of 202, for a total of 8 cohorts of 24-26 participants (divided equally into two groups per cohort). In the

team's prior work, 82% of those screened were eligible for participation: thus, we will aim to screen 246 WEH.

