- To evaluate reductions in PTSD symptoms, first, treatment response ( $\geq$  5-point reduction in symptoms) and clinically meaningful improvement (≥ 10-point reduction in symptoms) will be calculated for both immediate and 4-month follow-up. Potential covariates (e.g., demographic indicators; type, timing and amount of trauma exposure, including history of incarceration) will be screened for inclusion (included if p<.05). Change over time will be analyzed, using data from the three time points, using a mixed-effects repeated measures approach. This will also allow for a test of fixed (e.g., treatment group) and random (e.g., cohort) effects over time and conserves power by capitalizing on the longitudinal design. Reductions in PTSD will be examined using a modified Poisson distribution with robust variance, which tends to be less biased than a logit-based approach. Reductions in symptoms (measured continuously) will also be evaluated using a Gaussian distribution. Substance use will be evaluated using the TLFB, quantified as time to first use, days of use and relapse status (abstinent [did not use], lapse [used after study intervention but did not revert to regular use], or relapse [used substances for more than one third of days]). 34,35 Group x time contrasts will be tested. Identical analytic approaches will be used to examine secondary outcomes (suicidality, depression, and anxiety).
- To test for mediation effects, AGReMA (A Guideline for Reporting Mediation Analyses of Randomized Trials and Observational Studies) will be followed. A series of longitudinal structural equation models (SEM) will examine both direct and indirect effects by which change in mediators (emotion regulation, trauma-related guilt, trauma-related shame, moral injury and craving) are associated with change in PTSD, substance use, and secondary outcomes over time. Confidence intervals for indirect effects will be obtained through percentile bootstrap. SEM has the capacity to test for bidirectional

effects between PTSD symptoms and substance use. Model fit (e.g., Root Mean Square Error of Approximation) will be compared to find hypothesized paths that best fit the data.

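### Mediation paths are chosen by fit in the trial's own data, with intervals that ignore the choice and no required time order between mediator and outcome

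*Combined protocol and SAP*

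**What the plan says.** The mediation part of Section 3 (Data analytic plan) names five mediators: craving, moral injury, emotion regulation, and trauma-related guilt and shame. Change in these is to be examined for how it is "associated with change in PTSD, substance use, and secondary outcomes over time". Intervals for indirect effects come from a percentile bootstrap. Model fit, with RMSEA as the example, "will be compared to find hypothesized paths that best fit the data".

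The section gives no list of candidate models, no fit cut-off, no hold-out sample, no repetition of the selection inside the bootstrap, and no multiplicity rule for the mediation tests. It cites a reporting guideline for mediation analyses. Its one statement about two-way effects concerns PTSD symptoms and substance use, not mediators and PTSD.

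Subsection 1A.1 calls the mechanism aim exploratory, yet the power paragraph sizes the trial on it: "Sample size appropriate for mediation was derived from a percentile bootstrap method".

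On measurement, item 2g of Subsection 2.2 says that at four months "primary and secondary outcomes will be re-assessed, in addition to key covariates and recent negative life events", with no mention of mediators. The assessment overview (Table 3 in Subsection 2.3) marks footnote c at the 4-month visit in both arms, and that footnote reads "Mediators: emotion-regulation, self-compassion, moral injury, trauma-related guilt, trauma-related shame, craving, mindfulness".

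**The concern.** Two separate weaknesses bear on any statement about how MSC works.

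First, a path picked because it fits best in these data tends to be one where chance has enlarged the mediator–outcome association. A percentile bootstrap applied only to the chosen path does not know that others were tried, so its nominal 5% error need not hold.

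Second, the plan relates change to change without asking that the mediator move first. If MSC relieves PTSD and that relief then lowers shame or craving or improves emotion regulation, a model using both changes over the same interval can report those variables as mediators. This would happen even with no fit comparison.

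The primary treatment comparison is not affected. At stake is whether a reported mechanism is real, and whether its direction is right.

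**Working it through.** **Inputs from the documents.** Section 3 gives the planning values "with α=.05, β=.80, and the standard deviation bound at ±1.91" (β=.80 read as 80% power, test taken as two-sided), "a small-medium effect size of .3 was conservatively estimated" (metric not stated) and "This yielded a final sample size of 162". Subsection 2.6 gives three waves, Subsection 2.1 gives 101 per arm, and Section 3 names five mediators.

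**The plan's own figure.** The documents state no false-positive rate for mediation. The only figure to reproduce is 162, and it does not follow from 0.3:
- Two means, d=0.3: n per arm = 2(1.96+0.842)²/0.3² = 174.4, so 175 per arm and 350 in all.
- Correlation of 0.3: 85.
- Percentile-bootstrap mediation with both paths 0.3: about 125 by simulation; at 162 the power is 90%.
- Both paths near 0.26: 78% power at 162, but 0.26 is not in the documents.

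Retention agrees: 162/0.80 = 202.5, against 202. The gap in deriving 162 is a separate matter; 162 is used below as the analysable number.

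**Selection among placements.** Assumed: three waves, autoregression 0.6, baseline mediator–outcome correlation 0.3, participants independent. The candidates are post→post, post→4-month and 4-month→4-month. The indirect effect is a×b, where a is arm→mediator and b is mediator→outcome. With b=0, any interval excluding zero is a false claim. The best-fitting placement is chosen by likelihood ratio and its percentile interval taken from 400 resamples, over 1,500 trials per row.

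| Arm effect on mediator | Selected path | Worst of the three fixed paths | Ratio |
|---|---|---|---|
| 0 | 0.7% | 0.3% | 2.3 |
| 0.2 | 3.5% | 1.9% | 1.8 |
| 0.3 | 6.2% | 3.1% | 2.0 |
| 0.5 | 12.5% | 6.6% | 1.9 |
| 0.8 | 15.3% | 6.9% | 2.2 |

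The Monte Carlo standard error at 6.2% is √(0.062×0.938/1500) = 0.6 points, so that row is close to nominal. Other builds of the same scenario gave 11.5–13.6% at 0.5 and 14.6–16.6% at 0.8. The build with the highest rates had fixed paths at 4.9–7.1%, so its ratio lies between 13.6/7.1 = 1.9 and 16.6/4.9 = 3.4.

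**Selection among mediators instead.** Taking the best-fitting single mediator, with one leg of each indirect effect zero and inter-mediator correlation 0 to 0.7, gave 4.5–13.1% with five mediators and 6.0–15.5% with seven. With both legs zero it was 0.2–0.9%.

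**Multiplicity without selection.** For independent tests, 1−0.95⁵ = 22.6% and 1−0.95⁷ = 30.2%. Simulated rates of at least one false mediator, with one leg zero, were 14.4–26.1% for five and 17.3–34.9% for seven. Fixing the paths does not by itself deal with this.

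**Time order.** With PTSD driving the mediator (coefficient 0.3), same-interval paths gave false mediation in 18–19% of trials when the arm had no direct effect on the mediator, and in 78–95% when that effect was 0.5. The lagged path (post-intervention mediator to 4-month outcome) gave 0.5–7%.

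**Fit and direction.** Arm, mediator and outcome at one wave supply 3×4/2 = 6 variances and covariances. The forward model with a direct arm effect uses 3 paths + 1 arm variance + 2 residual variances = 6 parameters, and so does the reverse model. Both have df=0 and RMSEA 0, so fit says nothing about direction. In a three-wave cross-lagged model, fit preferred the true direction in 67% of trials at a lagged path of 0.1, 87% at 0.2 and 97% at 0.3.

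**Four-month measurement.** Item 2g of Subsection 2.2 omits the mediators; Table 3 in Subsection 2.3 includes them. The forward lagged path needs no 4-month mediator, but the reverse path does.

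**The case against.** The plan speaks of hypothesized paths, labels the aim exploratory and follows a reporting guideline; comparing hypothesized models is a legitimate exploratory use of SEM. That lowers the stakes, but the hypothesized paths are never listed, and neither a label nor a reporting guideline makes an interval valid after selection.

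A reader might infer that the plan carries a 12–17% false-mechanism rate. The documents do not support that. It needs arm effects on the mediator of 0.5–0.8, at or above the top of the 0.2–0.5 range cited in Section 3, and three placements that the plan does not name. At 0.3 the rate is about 6%, and at 0.2 it is below 5%.

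A reader might also infer that fit can never separate mediator-to-PTSD from PTSD-to-mediator. That is true of saturated same-wave models only; the plan names longitudinal models with three waves. Nor does it say that fit will decide that direction.

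The reverse-causation rates do not come from the fit rule. They come from the missing time order, and the plan does not commit itself to same-interval paths either.

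It would go too far to read item 2g of Subsection 2.2 as dropping mediators at four months: the list is incomplete but excludes nothing, and Table 3 includes them.

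Finally, making the lagged path the only model would discard mediation that occurs during the six-week course. That objection stands, and the fix below keeps the other paths in the report.

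**Conclusion.** The concern holds as two linked but distinct points. Choosing paths by fit and then using an unadjusted bootstrap roughly doubles to triples the false-positive rate for an indirect effect: about 6% at an arm effect on the mediator of 0.3 and 12–17% at 0.5–0.8, against about 3–7% for a fixed path. There is no excess over 5% when the arm has little or no effect on the mediator. Independently, with no time order required, same-interval paths can show false mediation in about 18% to over 90% of trials if PTSD drives the mediator, while the lagged path stays near nominal. Fit is imperfect evidence of direction and no evidence in saturated same-wave models.

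These sizes rest on assumed path effects, autoregression and candidate sets, and on independent participants. Cohort clustering was not modelled and would change them. The selection rule is a flaw in what is written, not only missing detail. It should be changed, although it concerns an exploratory aim and leaves the primary comparison intact.

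**What to change.** In the mediation part of Section 3, replace the fit-comparison sentence with the following:

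- List the candidate paths for each mediator before outcome data are seen, and report all of them whatever their fit. Use RMSEA as a check only; add, drop or reverse no path because of it.
- Include the lagged path from post-intervention mediator to 4-month outcome, adjusted for baseline and post-intervention outcome. Any claim of temporal order rests on this path.
- Report the reverse path, post-intervention outcome to 4-month mediator, as a sensitivity analysis. Report same-interval paths as associations.
- State a multiplicity rule across the five mediators, or label every indirect effect exploratory. One option is to test the five lagged paths for a given outcome at 0.05/5 = 1% each, which keeps the error for that family at or below about 5%.

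Reconcile item 2g of Subsection 2.2 with Table 3 in Subsection 2.3 so that mediators are measured at four months.

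The cost is SAP wording and one line in the procedures. Mechanism claims become more cautious, and the lagged path has less power for a mediator that acts within the six weeks; the associations over that interval are still reported.
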